1.7. Study Objectives

The primary study objective is to determine whether two injections of OO and thumb splint are superior to the use of only the joint splinting in reducing pain.

1) The primary study endpoint is to establish the improvement in DASH score from baseline.

2) Secondary objectives of this study are:

- Improvement in VAS Pain,
- Improvement in Grip Strength Function,
- Improvement in Tip Pinch Function.
- Improvement in the Kapandji Score.
- Improvement in the Nine-Hole Peg Test.

2. Investigational Plan

2.1. Study Design

This is a randomized, controlled, prospective evaluation comparing combined treatment with intra-articular ozone injections plus thumb splint with only the splint therapy. The maximum study duration for each subject will be 6 months. A total of 40 patients will be enrolled. These patients will meet specific inclusion and exclusion criteria, but can be generally characterized as patients with painful unilateral thumb OA who have been unable to achieve satisfactory pain relief with previous conservative OA treatment.

2.2. Eligibility Criteria

Inclusion criteria

- 1- Male or female at least 18 years of age at time of screening.
- 2- Ability to comply with study procedures and visit schedules and able to follow oral and written instructions.
- 3- Patients with symptomatic OA in one thumb joint from 3 months. If bilateral, the side with major symptoms will be considered.
- 4- A thumb joint radiograph showing a E-L grade of 1 to 3 and an absence of severe osteoarthritis (defined as advanced stage osteoarthritis, including large osteophytes, chronic fractures or bone remodeling, severe deformity or bone attrition, and/or bone-on-bone contact indicative of severe osteoarthritis/full thickness cartilage loss).
- 5- Has undergone at least one prior conservative OA treatment (e.g. physical therapy, simple analgesics).
- 6- Signed an ethics committee-reviewed approved informed consent form.

Exclusion criteria

- 1- Presence of clinically observed active infection or severe inflammation in the index trapeziometacarpal joint or skin disease/breakdown or infection in the area of the planned injection site of the index thumb joint.
- 2- Diagnosed with rheumatoid arthritis, Reiter's syndrome, psoriatic arthritis, gout, ankylosing spondylitis, or arthritis secondary to other inflammatory diseases; Human Immunodeficiency Virus (HIV), viral hepatitis; chondrocalcinosis, Paget's disease, or villonodular synovitis.
- 3- Diagnosed with leukemia, known presence of metastatic malignant cells, or ongoing or planned chemotherapeutic treatment.
- 4- Disease of cervical spine, shoulder or other upper extremity joints judged by the investigator to be contributing to the pain in the index thumb joint (e.g. radiculopathy, De Quervain S., ecc).
- 5- Untreated symptomatic injury of the index hand (e.g., acute traumatic injury, tendinopathy, nerve lesion).
- 6- Presence of surgical hardware or other foreign body intended to treat arthritis or cartilage-related pathology in the index thumb joint.
- 7- Presence of venous or lymphatic stasis in the index arm.
- 8- Orally administered systemic steroid use within 2 weeks prior to screening
- 9- Planned/anticipated surgery of the index hand during the study period.
- 10- Major surgery of the index hand within 12 months prior to screening.
- 11- Minor surgery (e.g. arthroscopy) of the index hand within 6 months prior to screening.

- 12- Any documented clinically significant degree of cognitive impairment or other condition, finding, or psychiatric illness at screening, which, in the opinion of the investigator, could compromise patient safety or interfere with the assessment of the safety and treatment effects of the study injection.
- 13- Pregnant or nursing mothers or women planning to become pregnant during the time they will be participating in the study.
- 14- Previously documented failed treatment with OOT or splint
- 15- Known drug or alcohol dependence currently or within the last year.
- 16- Use of any investigational drug or device within 30 days prior to screening.
- 17- Use of any investigational biologics within 60 days prior to screening.

2.3. Restricted Medications/Nonpharmacological Therapies

Patients will be advised that participation in the study will require them to abstain from certain medications and therapies for the entire 1 month period following the procedure. **In case of pain, it's possible to take Paracetamol 1000 mg 1 tablet (maximum dose 2 tablets per day).** In contrast, the following drugs and non-drug therapies should not be taken or used immediately upon enrollment (after signing informed consent) for the full 1 month period:

- Oral NSAIDs
- Topical NSAIDs (including plasters and patches) applied to the index hand
- Other topical pain therapies applied to the index hand (e.g., capsaicin, lidocaine, heat patches)
- Orally administered systemic corticosteroids
- Narcotics
- Centrally acting medications for analgesia

After completion of Month 1 visit, patients are allowed to take any medication they need to use. The following therapies should not be used beginning immediately upon enrollment (after signing informed consent) throughout the entire study follow-up:

- Intra-articular corticosteroids administered to the index hand
- Intra-articular HA administered to the index hand
- Other intra-articular therapy administered to the index hand
- Surgical procedure performed on the index hand

Subjects may utilize any medication they would like to use for concomitant OA treatment, unless listed above. General frequency and reason for use will be reported at each follow- up.

2.4. Study Assessments and Procedures

The table in Appendix A summarizes clinical study assessments, procedures, and information collected on case report forms (CRFs).

2.4.1. Screening Visit and Baseline Recording

Subject procedure flow is outlined in Appendix B.

2.4.1.1. General Pre-Screening

Patients with symptomatic OA in one trapezio-metacarpal joint, who have been unable to get satisfactory pain relief with prior treatment, will be pre-screened for eligibility. The investigator will keep a log listing all patients who are pre-screened for the study. Patients potentially meeting the inclusion and exclusion criteria will be asked to sign an informed consent form.

“Non-standard of care” test or procedure assessments specific to this Clinical Investigation may not be done before an informed consent has been signed.

2.4.1.2. Informed Consent

The patient must complete the informed consent process and sign and date the informed consent form prior to participation in this study, including completion of any non-standard-of-care procedures required for this Clinical Investigation. Designated center staff will explain the study purpose, data to be collected, how data will be used, time and travel commitments and other expectations of a study subject. The patient will be given the opportunity to discuss the study with the investigator, including any medical aspect of their disease and the study treatment. If the patient decides to participate, then he/she will sign and date the informed consent form along with the Investigator and other staff participating in the consent process; and the treatment visit will be scheduled.

A copy of the informed consent form will be given to the subject.

2.4.1.3. Confirm Eligibility

Screening assessments include:

- DASH questionnaire for index thumb joint
- X-Ray

2.4.1.4. Baseline Recording

During the screening visit, the following information will be obtained and recorded in the subject study record and CRFs for all subjects.

- Signed and dated original ICF

- Inclusion and exclusion criteria
- Demographics
- Relevant Medical history, baseline conditions and medication use

The following baseline assessments will be completed prior to treatment and after final eligibility confirmation (during injection visit and prior to the injection procedure itself).

- VAS
- Grip strength test
- Tip pinch strength test
- Kapandji Score
- Nine-Hole Peg Test

All preoperative procedures are to be completed within 28 days prior to the injection procedure.

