4.4. Bias Minimization

4.4.1. Randomization

The randomization plan will be produced using SAS v 9.4 or similar software. Balanced randomization with random block sizes (1:1, OOT plus splint:only splint) will be implemented. In the event that, post-randomization, no study treatment was given, randomization will not be reassigned and in this case will not count toward the overall sample size. Randomization will continue with the next case enrolled until the minimum sample size of 20 subjects is reached in both treatment groups. Subjects that have signed informed consent and are in screening process when the minimum study sample size is reached, will be randomized and treated per protocol provided that they found to be eligible. The enrollment activities will be monitored closely to limit number of these subjects. Randomization will be stratified by site, and each site will receive separate randomization plans using random predetermined block sizes that will remain undisclosed to the sites. The randomization file will be uploaded into the electronic data capture (EDC) system. Once the subject is enrolled into the EDC and has been identified as eligible for randomization, the randomization allocation will be visible within the EDC and viewable only by the un-blinded research associate. The subject will be treated according to the contents of the displayed randomization allocation.

5. Data collection, handling and retention

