Appendix A – Study Schedule

Assessments			Post Treatment fol	ow-up ¹		Study Exit
	Screening	Injections ² (1\week for 2 weeks) and/or Splint (2 months)	1 Month	3 Month	6 Month	
Visit window			± 7 days	± 7 days	± 7 days	
Informed Consent	X					
Eligibility	X					
Demographics	X					
Radiographs	X					
Follow-up			X	X	X	
Medication Use	X	X	X	X	X	
DASH	X		X	X	X	
VAS		X ³	X	X	X	
Grip strength and Tip pinch strength test	X		X	X	X	
Kapandji Score and Nine-Hole Peg Test	X		X	X	X	
Adverse Events		□	□	□	□	□
Study Exit Form		□	□	□	□	X

1: Follow-up assessments may consist of a structured telephone interview, electronic self-report or, if standard of care, an office visit. 2: The first injection should take place within 28 days of completed screening. 3: Questionnaires should be obtained prior to injection procedure

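### Baseline function tests have two conflicting time points, VAS and function baselines are not required to precede allocation, and the baseline DASH may be up to 28 days old

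*Combined protocol and SAP*

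**What the plan says.** **Function tests and VAS.** Section 2.4.1.4 lists VAS, grip, tip pinch, Kapandji and Nine-Hole Peg as baseline assessments made after final eligibility confirmation, "during injection visit and prior to the injection procedure itself". In Appendix A, the rows "Grip strength and Tip pinch strength test" and "Kapandji Score and Nine-Hole Peg Test" are marked under Screening and not under the treatment column. VAS is marked under the treatment column only, with the footnote "Questionnaires should be obtained prior to injection procedure".

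**DASH.** Section 2.4.1.3 and Appendix A place it at screening. It is not repeated before treatment. Section 2.4.1.4 adds: "All preoperative procedures are to be completed within 28 days prior to the injection procedure". Section 1.7 makes improvement in DASH from baseline the primary endpoint.

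**Allocation.** Under Section 4.4.1, once an enrolled subject "has been identified as eligible for randomization, the randomization allocation will be visible within the EDC". The same sentence limits that view to an unblinded research associate.

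**Medication.** Section 2.3 first describes the restriction as covering the month after the procedure, then bars the listed drugs "immediately upon enrollment (after signing informed consent) for the full 1 month period". The rule on stopping certain pain medication 48 hours before assessments appears only under follow-up visits, in Section 2.4.6.

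**The concern.** Sites cannot follow both the text and the schedule for four of the secondary measures, and the two time points can be up to four weeks apart.

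Under the Section 2.4.1.4 reading, the event that triggers these baselines (confirmed eligibility) is also the event that opens the allocation, and their order is not fixed. The comparator is a splint alone with no sham described, so patients learn their arm when treatment is arranged or given. A pain rating or a maximal-effort grip recorded after that can differ by arm for reasons unrelated to disease. Such a difference passes directly into the between-arm difference in change.

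For DASH the problem is different. The oldest baseline in the trial belongs to the primary endpoint, and it may have been recorded in a different medication state from follow-up. That blurs what a patient's change means, including change counted against the 10.83-point threshold in Section 7.2.

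**Working it through.** **1. Text against schedule**

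| Measure | Sections 2.4.1.3 and 2.4.1.4 | Appendix A | Agree? |
|---|---|---|---|
| DASH | Screening | Screening | Yes |
| VAS | Injection visit, before injection | Treatment column, before injection | Yes |
| Grip, tip pinch | Injection visit, before injection | Screening | No |
| Kapandji, Nine-Hole Peg | Injection visit, before injection | Screening | No |

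The contradiction covers four measures, all secondary under Section 1.7.

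**2. Order relative to allocation.** If Appendix A governs, DASH and the four function tests are taken at screening and only VAS is left at the treatment visit. If Section 2.4.1.4 governs, VAS and all four function tests are. Under either reading, no available passage makes completion of these baselines a condition for opening the allocation.

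**3. Age of the baseline at Month 1.** Inputs: the 28-day limit (Section 2.4.1.4 and Appendix A) and Month 1 ± 7 days counted from the injection (Section 2.4.6). Assumptions: a month is 30 days and the count starts at the first injection.

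- Injection-day measure: 30 − 7 = 23 to 30 + 7 = 37 days.
- DASH, screened on the injection day: 23 to 37 days.
- DASH, screened 28 days earlier: 23 + 28 = 51 to 37 + 28 = 65 days.
- DASH overall: 23 to 65 days.

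**4. Medication state.** If the restriction starts with the procedure, the screening DASH precedes it. If it starts at consent, Appendix A places consent and DASH in the same Screening column, so DASH falls at about its start and can still reflect earlier medication. A 30-day restriction starting at consent, with injection on day 28, would end 30 − 28 = 2 days after the first injection. The other wording covers the whole month after the procedure. Section 2.3 also ties free medication use to completion of the Month 1 visit. These statements are not equivalent.

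**5. Precision (illustration only).** The plan's figure reproduces: for 1 SD, two-sided 5% and 80% power, the normal approximation gives 16 per group (power 80.7%). A t-test with 16 per group has 78.1%. The documents give no baseline-to-follow-up correlation r for DASH. Assume that 1 SD refers to the raw score and that change is analysed. Then SD of change = √(2(1 − r)) in raw-score SDs.

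| Assumed r | SD of change | t-test power, 16 per group |
|---|---|---|
| 0.3 | 1.183 | 63.8% |
| 0.5 | 1.000 | 78.1% |
| 0.7 | 0.775 | 94.2% |

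The standard error ratio when r falls from r₁ to r₂ is √((1 − r₂)/(1 − r₁)). From 0.6 to 0.5 it is √(0.5/0.4) = 1.118, a 12% rise. From 0.7 to 0.5 it is √(0.5/0.3) = 1.291, a 29% rise. Nothing in the documents shows that 28 days would lower r by either amount.

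**The case against.** The strongest reply has five parts.

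- **Restricted view.** The EDC shows the arm to one role, so a pre-injection baseline need not follow the patient's knowledge of it. This stands as a limit: the documents leave the sequence open and do not show that baseline follows disclosure. They also do not say when the patient is told or who does the testing.
- **Order may be set elsewhere.** Baseline Recording precedes Randomization in the section numbering, and Appendix B, the subject flow, is available here by title only. Section order is not a rule. If Appendix B fixes the sequence, the allocation part of this point falls away, but the conflict with Appendix A remains.
- **The splint arm is covered.** A reader might infer that it has no baseline visit at all. The documents do not support that: the treatment column in Appendix A also covers the splint, and Section 2.4.1.2 schedules a treatment visit. What is missing is a time zero for that arm, because Section 2.4.6 counts follow-up from the injection.
- **Both arms share the DASH problem.** This is correct. An old baseline and a change in medication do not by themselves bias the comparison between arms. The responder percentage in Section 7.2 is also an additional description and not a stated primary test.
- **Precision loss is conditional.** Section 7.2 names t-tests or Mann-Whitney tests without saying whether change or follow-up values are compared. If follow-up values are compared, the age of the baseline costs no precision.

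**Conclusion.** The point holds as a scheduling contradiction on four secondary tests, an unguarded order between allocation and the VAS and function baselines, and an avoidably old baseline for the primary endpoint.

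Three stronger readings are tempting and are not supported:

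- **That the primary result is biased by baseline taken after allocation.** DASH is recorded at screening, so this mechanism does not reach it.
- **That the baseline DASH precedes the medication restriction.** That follows from only one of the two wordings in Section 2.3. What can be said is that it may reflect medication used before the restriction.
- **That the trial is declared open-label.** The term is not used. Patients' awareness of their arm is inferred from the absence of a sham, and the documents also use blinding terms without saying who is blinded.

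The firm sizes are the 28-day limit and the intervals to Month 1 of 23 to 65 days for DASH against 23 to 37 for an injection-day measure, given a 30-day month. The power and standard error figures rest on assumed correlations and show sensitivity only. Any shift in VAS or strength at baseline, and any loss of precision for DASH, cannot be quantified from the documents. Even so, the change is worth making before enrolment, because a missing or late baseline cannot be recovered.

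**What to change.** 1. Make Sections 2.4.1.3 and 2.4.1.4 and Appendix A agree on one baseline visit for both arms.
2. Complete DASH, VAS, grip, tip pinch, Kapandji and Nine-Hole Peg at that visit, and make their completion a condition in the EDC for opening the allocation.
3. Define time zero for the splint-only arm, so that the 28-day window and the follow-up visits are counted comparably in both arms.
4. Use the DASH from that visit as the baseline for change and responder status. No criterion in Section 2.2 sets a DASH cut-off, so eligibility is unaffected.
5. Reconcile the two starting points of the medication restriction in Section 2.3, and state whether the 48-hour rule in Section 2.4.6 applies to baseline. Repeating DASH does not settle this: if the restriction starts with the procedure, a DASH taken just before the injection also precedes it.
6. State who is blinded, when the patient is told the arm, and who performs the function tests.

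The cost is protocol and schedule wording, plus one repeated DASH questionnaire at an existing visit. Section 2.4.5 has splints made for every patient, so splint preparation gives no reason to open the allocation early.

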2.4.2. Randomization

Randomization will occur through a module in the CRF. Once randomization is complete and a treatment arm is assigned.

Eligible subjects will be randomized in a 1:1 ratio to one of following two treatment arms:

- Subject device: OOT plus thumb splint
- Comparator device: thumb splint

Details regarding randomization can be found in Section 4.4.1.

2.4.3. OOT Preparation

Take a disposable syringe with a needle of adequate size for the area to be treated. The syringe must have a capacity of 3 cc. The syringe is placed on the ozone-oxygen mix generator through a sterile filter, is loaded and is ready for use.

2.4.4. Injection Procedure

Administer the contents of the syringe as a single injection into the joint. The procedure for the injection involves the following steps:

1. Clean the injection area with an antiseptic solution.
2. Apply a local anesthetic on the injection site (optional). If local anesthetic is used, then a topical anesthetic, such as ethyl chloride, is recommended. Under no circumstances may the anesthetic be injected intra-articularly.
3. Position needle into the intra-articular space and confirm needle placement with an ultrasound image (if ultrasound guidance is being used).

4. Attach an empty syringe to the needle, aspirate all available joint fluid (aspiration volume must be recorded).
5. Transfer the syringe that contains the injection solution to the needle positioned at the injection site.
6. Inject all contents of the syringe into the synovial space of the joint. (Take care not to inject extra-articularly or into the synovial tissues and capsule).

A clear ultrasound image is to be taken to document needle placement in the synovial space. Any AEs associated with joint aspiration and injection procedure will be recorded. Additionally, any device processing issues will be recorded. Before discharge subjects will be instructed not to exceed their pre-injection physical activity level for 14 days post-injection.

2.4.5. Splinting procedure

An expert physiotherapist will create two personalized thermoplastic splint for every patients for the stabilizing of the TMJ (one for the day that has a functional aim and one for the night with the objective of TMJ rest). The splint maintains the pulp of the distal phalange of the index finger free for gripping with the other fingers and leaving the thumb in a functional position. Splints for TMJO provide external support to the joint, thereby stabilizing the adjacent joints capable of compensatory movements and maintaining the first joint space. The two splint will be used for 2 months.

2.4.6. Follow-up Visits

Follow-up assessment visits will be at the following intervals following the injection:

1 Month (\pm 7 days)

3 Month (\pm 7 days)

6 Month (\pm 7 days)

The following assessments and information will be collected at follow-up visits:

- DASH (all follow-up visits)
- VAS (all follow-up visits)
- Grip strength test (all follow-up visits)
- Tip pinch strength (all follow-up visits)
- Kapandji score (all follow-up visits)
- Nine-hole Peg test (all follow-up visits)
- Medication use (During the first 6-Month follow-up period, information on all medication usage will be collected)
- AEs (During the first 6-Month follow-up period, all AEs have to be reported.)

The study follow-up visits consist of a structured telephone interview and electronic self-report. The investigative center will contact the subject to complete the Follow-up, Adjunct Therapies and AE forms remotely.

Use of certain pain medication must be discontinued 48 hours prior to assessments (with the exception of aspirin taken for cardio protection). Aspirin in low dose would not be enough to affect any pain sensations. In addition, the low dose aspirin is supposed to be taken every day when taken for cardio-protection, so they should remain consistent on their regimen throughout the study. **In case of pain, it's possible to take Paracetamol 1000 mg 1 tablet (maximum dose 2 tablets per day).**

2.5. Subject Discontinuation and Withdrawal

2.5.1. Subject Deregistration

Subjects assigned a clinical investigation subject ID, but not having a study treatment administered, are considered deregistered and will not be considered as part of the intent-to-treat population and may be replaced (In case the subject is de-registered, a study exit form should be completed).

